16. STUDY DESIGN

16.1 Study Setting, Population and Patient Identification

This is a **single centre prospective randomized assessor blinded parallel group feasibility study** that will be undertaken in the Royal Devon and Exeter Dermatology department, Heavitree Hospital. The initial skin cancer clinic, surgical procedure and follow-up will all be undertaken within the department.

Our patient population is all patients attending the dermatology department for wide local excision as part of their skin cancer treatment and primary closure of the subsequent wound.

Clinicians will identify potential participants during routine practice at their clinic visit. Patients who fulfil the entry criteria will be invited at that appointment to take part and given a patient information sheet (PIS). They will be offered and consented for a further telephone call to discuss the study further.

Timing of Suture Removal to Reduce Scarring in Skin Surgery

Alternatively, when patients are telephoned to inform them of the date of their surgery, they will be informed of the study then. If patients are interested in the study, they will be offered a further telephone appointment with a member of the research team to discuss the study further, answer any questions and gain verbal consent. The PIS can be emailed or posted to the patient at their request. All patients will be offered a telephone call between clinic visit and their date of surgery for any questions to be answered and verbal consent to be gained.

16.2 Data Collection Prior to Surgery

On the day of their surgery, patients will be reminded of the trial and written consent will be sought by an appropriate member of the research team. Patients will then have their procedure performed and the randomization process will occur.

Data collection prior to procedure will include smoking status, history of immunosuppression, diagnosis of diabetes, full drug history (including steroid and anticoagulants use), age, ethnicity and history of keloid scarring or hypertrophic scarring. We will specifically ask for history of steroid use as this may affect the healing of scars post-surgery. This should all be recorded as standard practice and should not add additional workload, however this will be assessed in the feasibility study.

Data collection after the surgical procedure will include the size of the wound (maximal width and length), number of dermal sutures, type of dermal sutures used and number of percutaneous sutures used. Again, these should all be recorded as standard practice.

16.3 Surgical Procedure

The surgical procedure will be performed by one of the dermatological surgeons within the department.

All patients will have a standard local anaesthetic comprising lidocaine 1 or 2% with adrenaline 1:200000.

Patients will have their wide local excision with adequate margin as per regional guidance by an appropriately trained practitioner. The wound edges may be undermined if necessary or according to surgeon preference in order to achieve primary closure (documented accordingly).

The wound edges will be closely approximated with buried subcuticular interrupted vertical mattress sutures using 3/0 PDS (synthetic dissolvable mono filament suture) or equivalent. The number of sutures will be recorded. If the wound edges cannot be closely approximated then the patient will be withdrawn from the study. Interrupted percutaneous sutures will then be placed using ethilon 4/0 (non-absorbable, nylon monofilament suture) or equivalent in order to achieve optimal wound edge eversion.

16.4 Randomization and Blinding

Timing of Suture Removal to Reduce Scarring in Skin Surgery

Patients will be randomized into two groups following acceptance into the trial. A dermatology nurse, independent to the research trial and not involved in data collection or analysis, will use a random number generator to prepare 60 sealed envelopes, labelled 'participant 1' to 'participant 60'. These sealed envelopes will contain a slip of paper that either says 'suture removal at 7 days group' or 'suture removal at 10 days group'. During preparation of these envelopes using the random number generator, an odd number produced will be 'suture removal at 7 days group' and an even number will be 'suture removal at 10 days group'. The nurse who prepares these envelopes will be independent of the research trial to avoid any selection bias and maintain concealment. They will also have completed a 'Good Clinical Practice' (GCP) certificate. The surgeon and members of the research team involved in data gathering and analysis will be blinded to allocation.

After written consent to the trial has been gained, and excision of the lesion performed, the patient will leave the theatre room alongside one of our dermatology nurses/HCAs who is independent of the research team in order to maintain concealment and prevent selection bias. The patient and nurse/HCA will open one of the sealed envelopes, in numbered order, to reveal which arm of the trial they have been allocated to. The patient will be requested not to disclose which arm of the trial they were in. The theatre nurse or healthcare assistant will then discuss the post-operative wound care and timing of suture removal with the patient.

Patient blinding is not feasible as patients need to know which day to have their sutures removed post-surgery.

Before the patient leaves the department, an appointment will be booked with their GP for suture removal at either 7 or 10 days. If their GP does not have the capacity to remove the sutures on the given day, an appointment will be booked within the dermatology department on the given day for suture removal.

If the patient cannot attend the appointment for suture removal specifically on day 7 or 10, they will be removed from the study.

The envelope containing the slip of paper with the randomized trial arm will be re-sealed and placed in a larger envelope labelled with the participant number. The signed consent form will also be kept in this labelled participant envelope, which will be placed in a secure location in line with data governance.

Concealment of the trial arm allocation will be maintained until trial completion. However, the code could be broken in the event of a significant adverse event.

All recorded data will be anonymized prior to statistical analysis by the statistician.

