4. STUDY SUMMARY

Study Title	Timing of Suture Removal to Reduce Scarring in Skin Surgery
Study Design	Prospective randomized assessor blinded parallel group feasibility study
Planned Size of Sample	60
Follow up duration	3 months
Research Question/Aim(s)	In patients undergoing wide local excision and primary wound closure for treatment of skin cancer, does earlier removal of percutaneous sutures (7 days rather than 10 days) reduce the incidence of suture marks assessed at 3 months post-operatively.

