18.4 Sample Size

As this is a feasibility study, it will not be powered to find significant differences between the groups. Instead it is an opportunity to test the feasibility of collecting the specified outcome data and describing it in terms of central tendency (mean, median) and dispersion (standard deviation or interquartile range as appropriate). A feasibility study provides an excellent opportunity to uncover problems ahead of time, minimizing the need to adapt procedures or to develop contingency plans at short notice when the larger study is being conducted. A simple method for choosing a sample size for a feasibility study that ensures the discovery of potential problems with high confidence is employed here [9]. The method is used to determine the necessary sample size so that a problem is likely to be observed at least once during the course of the feasibility study. The emphasis therefore is on “problem detection” and not on the estimation of the “problem frequency.” If the probability (p) of a problem arising is 0.05, then a sample size of 59 would be required to detect at least one instance of the problem. The formula for calculating this is approx. $3/p$ participants if one wants to be approximately 95% certain that the problem will manifest itself at least once during the feasibility study. We will aim for 30 analysable cases per group in the final dataset giving a total of 60 cases.

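### The odd/even envelope rule in section 16.4 does not fix the arm totals, so read naturally it is unlikely to give the 30 per group aimed for in section 18.4; the cost is a modest loss of per-arm precision

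*Combined protocol and SAP*

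**What the plan says.** Section 16.4 (Randomization and Blinding) gives the allocation method. A dermatology nurse independent of the trial "will use a random number generator to prepare 60 sealed envelopes, labelled 'participant 1' to 'participant 60". The contents follow a parity rule: "an odd number produced will be 'suture removal at 7 days group' and an even number will be 'suture removal at 10 days group". After excision the patient leaves theatre with a nurse or healthcare assistant, and they "open one of the sealed envelopes, in numbered order". The section gives neither the range of the generator nor whether numbers can repeat, and no section mentions blocks, stratification, a quota or a list fixed in advance at 30 of each.

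Section 18.4 (Sample Size) sets the target: "We will aim for 30 analysable cases per group in the final dataset giving a total of 60 cases". The total itself is justified by problem detection. "If the probability (p) of a problem arising is 0.05, then a sample size of 59 would be required", so as to be "approximately 95% certain that the problem will manifest itself at least once during the feasibility study". Section 4 likewise plans a sample of 60.

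**The concern.** With 60 envelopes and 60 participants, 30 per group requires an exact 30/30 split. The written rule does nothing to produce one. If each envelope is filled from its own odd or even number, the arm sizes are left to chance, and the group size in section 18.4 is not something the method in section 16.4 can be relied on to deliver.

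What is at stake is precision within each arm. Section 17 plans descriptive summaries for each group with confidence intervals, and objective 2 in section 14 asks for complication and cosmesis data in each group. A smaller arm means a wider interval for that arm.

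**Working it through.** **Inputs**
- Envelopes: 60, opened in order (section 16.4).
- Target: 30 per group, 60 in total (section 18.4).
- Problem probability 0.05, confidence about 95% (section 18.4).
- Assumed: each draw is independent with a probability of 0.5 of being odd. The documents state neither.
- Assumed: no losses, so that the allocation rule is looked at alone.

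**Step 1. The plan's own figure.** n = ln(0.05)/ln(0.95) = 58.4, rounded up to 59. The approximation 3/p = 3/0.05 = 60. The chance of seeing the problem at least once is 1 − 0.95^59 = 0.9515 with 59 patients and 1 − 0.95^60 = 0.9539 with 60. The figure reproduces. It uses the total only, so the split between arms does not enter.

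**Step 2. The arm split.** Let X be the number allocated to 7 days, X ~ Binomial(60, 0.5).
- P(X = 30) = C(60,30)/2^60 = 0.103, so at least one arm is below 30 with probability 1 − 0.103 = 0.897.
- The SD of an arm size is √(60 × 0.5 × 0.5) = 3.87.
- The expected size of the smaller arm is 30 − E|X − 30| = 30 − 3.08 = 26.9.

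| Smaller arm | Probability |
|---|---|
| 29 or fewer | 89.7% |
| 27 or fewer | 51.9% |
| 25 or fewer | 24.5% |
| 24 or fewer | 15.5% |
| 22 or fewer | 5.2% |

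**Step 3. Sensitivity to the assumed probability.** If the generator ran over 1 to 9, P(odd) would be 5/9, and the chance of 30/30 would fall to about 7%. If instead it shuffled the numbers 1 to 60 without repeats, the parity rule would give exactly 30 of each. The text does not settle which applies.

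**Step 4. Cost in per-arm precision.** For a proportion of 0.5 (an assumed worst case), the 95% half-width is 1.96 × √(0.25/n):
- n = 30: 17.9 percentage points
- n = 27: 18.9
- n = 25: 19.6
- n = 24: 20.0

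The loss is about 1 point at the typical smaller-arm size and about 2 points at 24.

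**Step 5. Cost for a between-group difference.** Efficiency relative to 30/30 is 4 × n1 × n2/60²: 0.99 at 27/33, 0.96 at 24/36 and 0.93 at 22/38.

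**Step 6. What it would take under simple randomisation.** For both arms to reach 30, the total randomised would have to be about 70 for 80% probability, 74 for 90% and 77 for 95%, before any losses.

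**The case against.** Four points can be made for the plan as written, and most of them stand in part.

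- *Independence is inferred.* Section 16.4 gives a parity rule and no more, and a shuffle of 1 to 60 would meet the target exactly. This stands as a limit on certainty: the documents do not show that the draws are unrestricted. But neither a shuffle nor a quota is written, and simple draws are what a nurse following the text would most naturally do.
- *Thirty per group is an aim.* Section 18.4 uses the language of intention, and a 29/31 split is hardly a failure. This also stands. The 10.3% is the chance of meeting the figure literally; the smaller arm has at least 25 patients with probability 84.5%. Even so, the two sections should agree.
- *The consequence is small.* Agreed. Simple randomisation is valid and unbiased, section 17 plans no formal comparison, and estimates are imprecise even at 30 per arm.
- *Losses are the tighter constraint.* Section 16.4 also says "If the patient cannot attend the appointment for suture removal specifically on day 7 or 10, they will be removed from the study", and section 16.5 and Appendix 13 withdraw patients whose sutures are kept in. With only 60 envelopes, any such loss makes 30 analysable per group impossible under any allocation method. This is correct, and it limits what a better list can achieve.

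A reader might also infer that the 10-day arm's rate would size the definitive trial, so that a small 10-day arm is a particular danger. The documents do not say this. Objective 1 speaks of the standard deviation of the outcome, and section 17 of differences and their standard deviation. The probabilities above are for whichever arm turns out smaller, and the 10-day arm is equally likely to be the larger.

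**Conclusion.** The point holds as a mismatch between sections 16.4 and 18.4, with a modest consequence. On the natural reading, and assuming an even chance per draw and no losses, the allocation rule gives 30/30 about one time in ten. The typical smaller arm is about 27, and there is a 15.5% chance of 24 or fewer. At an assumed 50% rate this costs roughly 1 to 2 percentage points of half-width in the smaller arm.

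It would be tempting to conclude that the sample size is undermined or the comparison compromised. Neither follows: the 59/60 calculation depends only on the total, and chance imbalance in numbers introduces no bias. The change is still worth making because it is nearly free and makes the allocation match the stated group size.

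**What to change.** In section 16.4, have the same independent nurse prepare the envelopes from a computer-generated list restricted to 30 per arm. Use permuted blocks of randomly varying size, chosen so that the list closes at 30 and 30, with block sizes withheld from the surgeon and research team. Blocks also keep the arms close if recruitment stops early. The rest of the envelope procedure stands.

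If simple randomisation is preferred, or if a restricted list was always intended, say so: restate section 18.4 as about 30 per group in the first case, and describe the restriction in section 16.4 in the second.

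In either case, section 18.4 should describe the figure per group as randomised rather than analysable. A restricted list secures 30 randomised per arm; the shortfall from removals after allocation is separate and needs its own treatment.

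The cost is a sentence in each section and a different list. The one downside is that allocations near the end of a block are slightly more predictable. Varying, undisclosed block sizes limit this, as does opening envelopes after excision and away from the blinded surgeon.

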22.12 Appendix 12 – GP letter

Dermatology Department
Heavitree Hospital
[name]
Exeter
[name]
[contact]

INSERT DATE

Dear INSERT NAME OF GP

TIMING OF SUTURE REMOVAL TO REDUCE SCARRING IN SKIN SURGERY

Re: PARTICIPANT DETAILS

The above named person has kindly agreed to take part in this research study. The objective of the study is to determine whether suture removal at day 7 or day 10 post skin surgery will affect suture marks and overall cosmesis of scars.

Your patient has been chosen to take part because they have been booked for a wide local excision for their skin cancer surgery.

Should you have any queries about this, please do not hesitate to contact me on the details above.

Yours Sincerely,

[name]
Academic Foundation Doctor
Royal Devon and Exeter Hospital NHS Trust

Timing of Suture Removal to Reduce Scarring in Skin Surgery

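### Revealing the arm before booking an exact-day removal can cost the 10-day arm more patients, because day 10 falls on a weekend after Wednesday or Thursday surgery

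*Combined protocol and SAP*

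**What the plan says.** Section 16.4 (Randomization and Blinding) sets the order of events. After consent and excision, the arm is revealed: "The patient and nurse/HCA will open one of the sealed envelopes, in numbered order, to reveal which arm of the trial they have been allocated". The removal visit is arranged afterwards, before the patient goes home: "an appointment will be booked with their GP for suture removal at either 7 or 10 days". If the GP has no capacity, the fallback changes the place but not the date: "an appointment will be booked within the dermatology department on the given day for suture removal". The exact day is then enforced: "If the patient cannot attend the appointment for suture removal specifically on day 7 or 10, they will be removed from the study".

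The same section fixes the supply of allocations. An independent nurse "will use a random number generator to prepare 60 sealed envelopes", with odd numbers giving the 7-day arm and even numbers the 10-day arm. Section 18.4 (Sample Size) sets the target: "We will aim for 30 analysable cases per group in the final dataset giving a total of 60 cases".

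The text reviewed does not define day 0 formally. The GP letter (Appendix 12) describes the question as "whether suture removal at day 7 or day 10 post skin surgery will affect suture marks", which most naturally counts days after surgery. The text does not mention weekends or public holidays, the weekdays on which surgery is done, or whether either site removes sutures at weekends. Nothing requires a check before allocation that both dates can be booked.

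**The concern.** Because the two intervals differ by three days, they meet the working week differently. A 7-day interval always returns to the weekday of surgery, and a 10-day interval does not. With booking done after allocation and no window, a closed clinic could end a patient's participation, or lead to removal on another day, for a reason that depends on the arm.

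Two objectives in section 14 are exposed. Objective 5 describes follow-up and adherence: closure at weekends could be read as poorer adherence to later removal. Objective 1 needs the suture-mark rate to size the definitive trial, and the 10-day arm supplies the comparator rate, so losses there make it less precise.

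The study might also be unable to diagnose the cause. The data collection form (Appendix 8) has no field for date of surgery, actual date of removal, or reason for leaving the study.

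**Working it through.** **Inputs from the protocol.** Removal at 7 or 10 days, exact day, booking after allocation, 60 envelopes (section 16.4); target of 30 analysable cases per group (section 18.4).

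**Assumptions, because the documents are silent.** Surgery is on weekdays; f is the share of surgery done on Wednesday or Thursday; no weekend removal at the GP or the department; a patient with no available appointment is treated as unable to attend.

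**Step 1: the plan's own figure.** Section 18.4 states "If the probability (p) of a problem arising is 0.05, then a sample size of 59 would be required". To see such a problem at least once with 95% probability, n = ln(0.05)/ln(0.95) = 58.40, rounded up to 59. The shortcut 3/p gives 3/0.05 = 60. The figure reproduces. The present point does not depend on it, but it shows that 60 carries no allowance for losses.

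**Step 2: weekdays, surgery as day 0.** 7 mod 7 = 0 and 10 mod 7 = 3, so day 7 keeps the weekday and day 10 moves it on by three.

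| Surgery | Day 7 | Day 10 |
|---|---|---|
| Mon | Mon | Thu |
| Tue | Tue | Fri |
| Wed | Wed | **Sat** |
| Thu | Thu | **Sun** |
| Fri | Fri | Mon |

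Day 10 is on a weekend for 2 of 5 surgery days (40%), day 7 for 0 of 5.

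**Step 3: sensitivity to the day count.** If surgery were day 1, day 7 would fall on Sunday after Monday surgery (1 of 5), and day 10 on Saturday or Sunday after Thursday or Friday surgery (2 of 5). The 10-day arm is still hit harder, but the 7-day arm is hit too.

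**Step 4: possible size.** Taking 30 allocated to the 10-day arm for illustration, analysable cases there = 30 × (1 − f). The 7-day arm stays at 30 as far as this mechanism goes.

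| f | Lost, 10-day arm | Left, 10-day arm | Total left |
|---|---|---|---|
| 0 | 0 | 30 | 60 |
| 0.2 | 6 | 24 | 54 |
| 0.4 (even Mon–Fri) | 12 | 18 | 48 |
| 0.6 | 18 | 12 | 42 |
| 1 | 30 | 0 | 30 |

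The percentages are firmer than the counts. Thirty per group is an analysable target, not the number allocated. Odd/even allocation of 60 envelopes, with no balancing stated, gives 30 per arm on average but exactly 30/30 with probability C(60,30)/2^60 = 0.103.

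**Step 5: effect on precision, for f = 0.4.** For a suture-mark rate of 50% (assumed, as the widest case), the 95% half-width by the normal approximation is 1.96 × √(0.25/30) = 17.9 percentage points with 30 patients and 1.96 × √(0.25/18) = 23.1 points with 18. For a problem that can be seen only in patients who stay in the study, the chance of seeing it at least once at p = 0.05 falls from 1 − 0.95^60 = 0.954 to 1 − 0.95^48 = 0.915.

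**The case against.** The strongest reply is that the documents show a calendar fact, not a loss. No list days or opening hours are given, and section 16.4 commits the department, without qualification, to the given day when the GP cannot provide it. If the department can do so at weekends, nothing is lost. The flow chart and the patient information sheet were not in the text reviewed and may say more. This stands: the size is undetermined.

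Second, the 7-day arm is not immune. Public holidays and patients' own commitments can affect day 7, and a day-1 count would put some day-7 visits on a Sunday. This also stands. The asymmetry belongs to the weekend mechanism under a day-0 count.

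Third, a feasibility study exists to expose such problems. Section 18.4 stresses finding problems, objective 8 anticipates extra clinic slots, and section 17 plans no formal comparison of outcomes. This stands in part. A booking failure is genuine feasibility information, but only if its cause is recorded, and Appendix 8 has nowhere to record it. This cause can also be foreseen without enrolling anyone.

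Fourth, the harm might be laid at the door of removing patients after randomisation. Keeping them in the analysis as allocated, with the actual removal day recorded, would deal with much of the bias. It would not make a weekend appointment available, so the scheduling question remains.

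Finally, checking both dates first screens out some logistical failures and could make adherence look better than in routine practice. That is a fair cost. It is met by logging those screened out.

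**Conclusion.** The point holds as a conditional one. Section 16.4 combines allocation before booking, an exact day and removal from the study in a way that can produce arm-dependent loss after randomisation. With surgery as day 0, the weekend part of that loss falls on the 10-day arm.

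Its size rests on two undocumented facts: whether any surgery is done on Wednesday or Thursday, and whether the GP or the department removes sutures at weekends. The range is 0% to 100% of the 10-day arm, with 40% under even Monday-to-Friday surgery and no weekend removal. Since 60 envelopes serve a target of 60 analysable cases, any such loss also leaves the target short.

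A reader might infer that the 10-day arm cannot be delivered, that 12 of 30 patients will be lost, or that only the 10-day arm can lose patients to the exact-day rule. The documents support none of these. The first needs closed weekends and surgery confined to Wednesday and Thursday; the second is an illustration from assumed inputs applied to a target number; the third ignores holidays, patient availability and the undefined day count.

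This is a change worth making because it is cheap and preventive, not because a loss has been shown.

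**What to change.** Leave both removal days unchanged and amend section 16.4 as follows.

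- Define day 0.
- Before the envelope is opened, ideally when the surgery date is confirmed, have the independent nurse or HCA confirm that appointments on both the day-7 and the day-10 dates can be booked, at the GP or in the department, and that the patient could attend either.
- Randomise only patients who pass this check. Others do not use an envelope.
- Record, as feasibility outcomes, the number not randomised for this reason and the weekday of surgery. Add the weekday to Appendix 8 and keep a log for those not randomised.

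Exclusion for lack of an appointment then happens before allocation and applies equally to both arms. Concealment is kept, because nobody knows the arm at the time of the check. If weekend removal is already available, a sentence in section 16.4 saying so removes most of the concern. How a due date on a closed day should be handled clinically is for the sponsor to decide.

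I would not steer surgery to particular weekdays: section 19.1 presents the trial as pragmatic and part of routine care, and the check does the work without that.

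The cost is a short amendment and one calendar check per patient. Recruitment may be slightly slower, and some consented patients will not be randomised. Adherence among those randomised should be reported alongside the log, so that it is not taken as the rate in all eligible patients.
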